		
Adherence will be measured as 'Proportion of days covered = (Number of days covered by any ART, excluding ritonavir and cobicistat) ÷ (total days)*100'[27] every six months
 
Individuals with >80% of days covered will be classified as 'adherent' and individuals with ≤80% of days covered will be classified as 'non-adherent'[27]
	
	CD4 cell count	Categorized as <200, 200-499, ≥500 cells/mm ³	Baseline and follow-up
	PPSV23 vaccination	NDC and CPT codes listed in Appendix Table 8	Baseline and follow-up
	Annual CD4 laboratory test	
CD4 laboratory tests will be identified by CPT codes listed in Appendix Table 9
 
Individuals who have at least one CD4 laboratory test performed during each year of follow-up
	Baseline and follow-up
	Annual viral load laboratory test	
Viral load laboratory tests will be identified by CPT codes listed in Appendix Table 10
 
Individuals who have at least one viral load laboratory test performed during each year of follow-up
	Baseline and follow-up
	Respiratory virus season	Respiratory virus season occurs between October 1 and April 30	Follow-up
Sensitivity analysis outcome	All-cause pneumonia not associated with HIV	ICD-9-CM or ICD-10-CM codes listed in Appendix Table 11	Follow-up

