Several stratified analyses will be conducted. PPSV23 is recommended for PLWH and feasibility data provided by Komodo suggest that one in four PWLH who received PCV13 during 2014-2015 also received PPSV23 within two years. Rather than censor or exclude

individuals who receive PPSV23, we will calculate PCV13 VE among PWLH who have/have not received PPSV23 before and during the study period.

Feasibility assessments from Komodo indicate that approximately 25% of PWLH have at least one CD4 cell count or percentage laboratory result available. Therefore, we will calculate PCV13 VE among the subset of PWLH who have a CD4 cell count during the baseline period or follow-up, and potentially stratify by CD4 category using each patient's lowest value during the study.

Additional VE stratifications by ART adherence during follow-up, year of HIV diagnosis, and age will be assessed for feasibility as well, as these affect patients' immune status and immune reconstitution. Due to possible waning of the VE and different lengths of follow-up by index year, VE stratification by year of HIV diagnosis will be restricted to the first 3 years of follow-up.

A sensitivity analysis will also be conducted. In this analysis, causes of pneumonia that are characteristic of HIV, for example pneumonia due to cytomegalovirus, mycobacteria, and fungi, will be excluded from our definition of all-cause pneumonia.

Residual confounding of our VE estimates due to inadequate control for health care seeking behavior and immune status in our analyses will be explored. To do so, we will employ a negative control exposure and a negative control outcome. Potential negative control exposures include vaccinations that are recommended for PLWH but would not be expected to have any protective effect against the pneumonia outcomes of interest. If residual confounding does not exist, the negative control vaccine would not have an effect on the pneumonia outcomes. However, if the analysis demonstrates that the negative control vaccine protects against these outcomes, this suggests the presence of residual confounding.

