	481	Pneumococcal pneumonia [Streptococcus pneumoniae pneumonia]	J18.1 J13	Lobar pneumonia, unspecified organism Pneumonia due to Streptococcus pneumoniae
	482	Pneumonia due to Klebsiella pneumoniae	J15.0	Pneumonia due to Klebsiella pneumoniae
	482.1	Pneumonia due to Pseudomonas	J15.1	Pneumonia due to Pseudomonas
	482.2	Pneumonia due to Hemophilus influenzae [H. influenzae]	J14	Pneumonia due to Hemophilus influenzae
	482.3	Pneumonia due to Streptococcus , unspecified	J15.4	Pneumonia due to other streptococci
	482.31	Pneumonia due to Streptococcus , group A	J15.4	Pneumonia due to other streptococci
	482.32	Pneumonia due to Streptococcus , group B	J15.3	Pneumonia due to Streptococcus , group B
	482.39	Pneumonia due to other Streptococcus	J15.4	Pneumonia due to other streptococci

PFIZER CONFIDENTIAL

CT24-WI-GL02-RF02 5.0 Non-Interventional Study Protocol Template For Secondary Data Collection Study 01-Aug-2023

Page 38 of 46

	482.4	Pneumonia due to Staphylococcus, unspecified	J15.20	Pneumonia due to staphylococcus, unspecified
	482.41	Methicillin susceptible pneumonia due to Staphylococcus aureus	J15.211	Pneumonia due to Methicillin susceptible Staphylococcus aureus
	482.42	Methicillin resistant pneumonia due to Staphylococcus aureus	J15.212	Pneumonia due to Methicillin resistant Staphylococcus aureus
	482.49	Other Staphylococcus pneumonia	J15.29	Pneumonia due to other staphylococcus
	482.81	Pneumonia due to anaerobes	J15.8	Pneumonia due to other specified bacteria
	482.82	Pneumonia due to escherichia coli [E. coli]	J15.5	Pneumonia due to Escherichia coli
	482.83	Pneumonia due to other gram-negative bacteria	J15.6	Pneumonia due to other aerobic Gram-negative bacteria
	482.84	Pneumonia due to Legionnaires' disease	A48.1	Legionnaires' disease
	482.89	Pneumonia due to other specified bacteria	J15.8	Pneumonia due to other specified bacteria
	482.9	Bacterial pneumonia, unspecified	J15.9	Unspecified bacterial pneumonia
	483	Pneumonia due to mycoplasma pneumoniae	J15.7	Pneumonia due to Mycoplasma pneumoniae
	483.1	Pneumonia due to chlamydia	J16.0	Chlamydial pneumonia
	483.8	Pneumonia due to other specified organism	J16.8	Pneumonia due to other specified infectious organisms
	484.1	Pneumonia in cytomegalic inclusion disease	B25.0	Cytomegaloviral pneumonitis

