	484.3	Pneumonia in whooping cough	A37.91 A37.01 A37.11 A37.81	Whooping cough, unspecified species with pneumonia Whooping cough due to Bordetella pertussis with pneumonia Whooping cough due to Bordetella parapertussis with pneumonia Whooping cough due to other Bordetella species with pneumonia
	484.5	Pneumonia in anthrax	A22.1	Pulmonary anthrax
	484.6	Pneumonia in aspergillosis	B44.0	Invasive pulmonary aspergillosis
	484.7	Pneumonia in other systemic mycoses	J17	Pneumonia in diseases classified elsewhere
	484.8	Pneumonia in other infectious diseases classified elsewhere	J17 B77.81	Pneumonia in diseases classified elsewhere Ascariasis pneumonia
	485	Bronchopneumonia, organism unspecified	J18.0	Bronchopneumonia, unspecified organism

PFIZER CONFIDENTIAL

CT24-WI-GL02-RF02 5.0 Non-Interventional Study Protocol Template For Secondary Data Collection Study 01-Aug-2023

Page 39 of 46

	486	Pneumonia, organism unspecified	J18.8 J18.9	Other pneumonia, unspecified organism Pneumonia, unspecified organism
	487	Influenza with pneumonia	J10.00 J10.08 J11.00 J11.08 J12.9	Influenza due to other identified influenza virus with unspecified type of pneumonia Influenza due to other identified influenza virus with other specified pneumonia Influenza due to unidentified influenza virus with unspecified type of pneumonia Influenza due to unidentified influenza virus with specified pneumonia Viral pneumonia, unspecified
	510.x			Empyema
	510	Empyema with fistula	J86.0	Pyothorax with fistula
	510.9	Empyema without mention of fistula	J86.9	Pyothorax without fistula
			J85.1	Abscess of lung with pneumonia
	136.3	Pneumocystosis	B59	Pneumocystosis
Pneumococca 1	481	Pneumococcal pneumonia	J13	Pneumonia due to Streptococcus pneumoniae
	482.9 + 041.2	Bacterial pneumonia, unspecified + pneumococcus	J15.9 + B95.3	Unspecified bacterial pneumonia + Streptococcus pneumoniae
	485 + 041.2	Bronchopneumonia, organism unspecified + pneumococcus	J18.0 + B95.3	Bronchopneumonia, unspecified organism + Streptococcus pneumoniae
	486 + 041.2	Pneumonia, organism unspecified + pneumococcus	J18.8 + B95.3 J18.9 + B95.3	Other pneumonia, unspecified organism + Streptococcus pneumoniae Pneumonia, unspecified organism + Streptococcus pneumoniae
	510.x + 041.2			Empyema + pneumococcus
	510 + 041.2	Empyema with fistula + pneumococcus	J86.0 + B95.3	Pyothorax with fistula + Streptococcus pneumoniae

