484.3	Pneumonia in whooping cough	A37.91 A37.01 A37.11 A37.81	Whooping cough, unspecified species with pneumonia Whooping cough due to Bordetella pertussis with pneumonia Whooping cough due to Bordetella parapertussis with pneumonia Whooping cough due to other Bordetella species with pneumonia
484.5	Pneumonia in anthrax	A22.1	Pulmonary anthrax
		J17	Pneumonia in diseases classified elsewhere
484.8	Pneumonia in other infectious diseases classified elsewhere	J17 B77.81	Pneumonia in diseases classified elsewhere Ascariasis pneumonia
485	Bronchopneumonia, organism unspecified	J18.0	Bronchopneumonia, unspecified organism
486	Pneumonia, organism unspecified	J18.8 J18.9	Other pneumonia, unspecified organism Pneumonia, unspecified organism
487	Influenza with pneumonia	J10.00 J10.08 J11.00 J11.08 J12.9	Influenza due to other identified influenza virus with unspecified type of pneumonia Influenza due to other identified influenza virus with other specified pneumonia Influenza due to unidentified influenza virus with unspecified type of pneumonia Influenza due to unidentified influenza virus with specified pneumonia Viral pneumonia, unspecified

510.x		Empyema		
510	Empyema with fistula	J86.0	Pyothorax with fistula	
510.9	Empyema without mention of fistula	J86.9	Pyothorax without fistula	
		J85.1	Abscess of lung with pneumonia	

Table 12. National Drug Codes and CPT® Codes for Identifying Recombinant Zoster Vaccination

Code	Type	Description
58160082801	NDC	Shingrix
58160082803	NDC	Shingrix
50090514700	NDC	Shingrix
58160081912	NDC	Shingrix
58160082311	NDC	Shingrix
50090337200	NDC	Shingrix
90750	CPT	Zoster Vaccine Recombinant, Adjuvanted, Suspension for Intramuscular Injection

Table 13. National Drug Codes for Identifying Candidiasis Antifungals (see excel)

Table 14. Diagnosis Codes for Identifying Opportunistic Infections (see excel)

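### The code list for the HIV-pneumonia sensitivity analysis drops systemic mycoses under ICD-9 (484.7) but keeps the paired ICD-10 code J17, so fungal pneumonia coded J17 still counts

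*Protocol*

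**What the plan says.** Protocol section 9.7 announces one sensitivity analysis: "A sensitivity analysis will also be conducted". The section then states that "causes of pneumonia that are characteristic of HIV, for example pneumonia due to cytomegalovirus, mycobacteria, and fungi, will be excluded from our definition"; the definition meant is the one for the all-cause outcome. Protocol Table 1 (section 9.3) names the outcome "All-cause pneumonia not associated with HIV" and points to Appendix Table 11. SAP Table 5.2 points to SAP Table 7.6, which has the same codes.

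The starting list is the all-cause block of Protocol Appendix Table 4 (SAP Table 7.4). There, ICD-9 484.7, "Pneumonia in other systemic mycoses", is paired with J17. The next row, 484.8, "Pneumonia in other infectious diseases classified elsewhere", is paired with J17 and B77.81.

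Table 11 no longer has 484.7 or its description. J17, "Pneumonia in diseases classified elsewhere", is still listed, once with nothing in the ICD-9 cell and again beside 484.8. Table 11 also opens with the row 480-486 487.0, carried over from Table 4.

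**The concern.** The stated definition excludes fungal pneumonia, but the list removes one fungal cause only on its ICD-9 side. For the other targeted causes both halves of the pair are gone. The J17 row therefore looks like an incomplete deletion rather than a choice, and because it is repeated in the SAP it is unlikely to be an artefact of how the tables were read.

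This is the only outcome sensitivity analysis in the plan. It should show whether the all-cause result changes once HIV-characteristic pneumonia is set aside. If some of that pneumonia stays in, the comparison is less sharp than described, and what is removed differs between ICD-9 and ICD-10 time. Section 9.7 does not state that the analysis is a check on immune status. That is a reasonable inference, because the same section says CD4 values will be missing for most patients.

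**Working it through.** No sample-size or power arithmetic applies. The check compares the all-cause rows of Table 4 with those of Table 11, and then asks what the range row could bring back.

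**1. Itemised codes, Table 4 against Table 11**

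- ICD-9: 39 codes fall to 34. Dropped (5): 136.3, 483, 484.1, 484.6, 484.7.
- ICD-10: 47 unique codes fall to 43. Dropped (4): B25.0, B44.0, B59, J15.7.
- None is added. Five deletions on one side and four on the other leave one pair half-deleted: 484.7/J17.

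| Cause | Pair in Table 4 | ICD-9 in Table 11 rows | ICD-10 in Table 11 rows |
|---|---|---|---|
| Cytomegalovirus ("Pneumonia in cytomegalic inclusion disease") | 484.1 / B25.0 | removed | removed |
| Aspergillosis | 484.6 / B44.0 | removed | removed |
| Pneumocystis | 136.3 / B59 | removed | removed |
| Other systemic mycoses | 484.7 / J17 | removed | **kept, twice** |
| Mycoplasma | 483 / J15.7 | removed | removed |

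The only other blank ICD-9 cell beside an ICD-10 code, at J85.1, is already blank in Table 4. The blank beside J17 appears only in Table 11.

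**2. The row 480-486 487.0**

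Applied literally, it would readmit four of the five dropped ICD-9 codes: 483, 484.1, 484.6 and 484.7. Only 136.3 lies outside it. Read as a heading, it readmits none. Neither document says which is meant, but the layout favours a heading:

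- The same row stands over the unspecified-cause list in Table 5, whose ICD-9 items are only 480.9, 482.9, 485 and 486. A literal range would put 481, pneumococcal pneumonia, into an unspecified-cause outcome, although Table 5 lists 481 in a separate group.
- The rows 510.x, 421.x and 730.0x likewise sit above their own itemised codes.

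**3. Calendar span affected**

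The earliest index date is July 2014 (first HIV code in January 2014 plus six months) and data end in September 2022. Counting both end months, that is 6 + 84 + 9 = 99 months. The documents do not give the ICD-10 start. Assuming October 2015, ICD-9 covers 6 + 9 = 15 months and ICD-10 covers 99 − 15 = 84. Moving the assumed start by a month moves both figures by one. These are calendar months, not person-time.

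**4. Truncated ICD-9 codes**

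The range row has 487.0, but the itemised row for influenza with pneumonia has 487. The rows 480, 482, 482.3, 482.4 and 510 look shortened in the same way. The same forms appear in Table 4, so this is a general tidying point.

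**5. A neighbouring mismatch**

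Section 9.7 names mycobacteria, but no itemised row in Table 4 or Table 11 does. The rows removed include Mycoplasma, which section 9.7 does not mention.

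**The case against.** The strongest reply is that J17 is non-specific. Table 4 pairs it with both 484.7 and 484.8, and 484.8 is rightly kept, so keeping J17 could be the only way to keep the legitimate events. This stands in part. J17 cannot be split by the code alone, and deleting only the orphan row would change nothing, because J17 remains under 484.8. But it does not reconcile the list with section 9.7: the plan has no rule for setting aside fungal J17 events.

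A second reply is that the effect is probably slight, and that the plan addresses immune status elsewhere, through negative controls, the CD4 subset and strata by antiretroviral adherence. The secondary pneumonia outcomes also itemise no J17, cytomegalovirus or fungal codes. That is fair and limits the weight of the point.

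A reader might infer more: that cytomegalovirus and aspergillosis pneumonia also still count, or that no reading of Table 11 gives the intended ICD-9 exclusions. The documents do not support either. Both causes are gone from the itemised rows in both coding systems, and with the range row taken as a heading, all of 484.1, 484.6, 484.7 and 136.3 are out. The shortened codes do not change this: each row's description identifies the cause, and neither document specifies prefix matching.

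**Conclusion.** The point holds for J17. Of the four causes removed that fit the stated aim (leaving Mycoplasma aside), one, systemic mycoses, stays in the outcome in ICD-10 time through J17. That is up to 84 of 99 calendar months if ICD-10 began in October 2015. The other three are removed under both coding systems. Only if the range row were applied literally would cytomegalovirus, aspergillosis and systemic mycoses return, and then only for ICD-9 claims, at most 15 of the 99 months on the same assumption.

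The documents give no counts for J17, so the effect on VE cannot be calculated and may be small. It would be going too far to say that agreement between the main and sensitivity results is built in. What can be said is that the list does not yet match its own definition, and it should do so before the outcome is programmed.

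**What to change.** In Protocol Appendix Table 11 and SAP Table 7.6:

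1. Delete the J17 row that has no ICD-9 code.
2. Count J17 under 484.8 only when the same admission, or the same-date outpatient claim, carries no fungal, mycobacterial or cytomegalovirus code. SAP section 5.3.1 already uses this admission and date rule for combination codes. The simpler alternative is to drop J17 from this outcome altogether.
3. Label the row 480-486 487.0 a heading, or replace it with explicit full ICD-9 codes that omit 484.1, 484.6 and 484.7.
4. Write the shortened ICD-9 codes in full, for example 487.0 for 487, and make the same correction in Table 4.
5. While the table is open, state whether removing Mycoplasma is intended and how mycobacterial pneumonia is identified.

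The cost is one table edit per document, plus item 4 in Table 4 (SAP Table 7.4), with no new data. The conditional rule needs a short list of fungal, mycobacterial and cytomegalovirus codes. Table 4 gives a start; the opportunistic-infection codes in Appendix Table 14 may supply more, but its contents are in a separate file. The downside is that a few non-fungal J17 events may be lost, more of them if J17 is dropped outright.

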ANNEX 1. LIST OF STAND ALONE DOCUMENTS

If there is no document to be listed, delete the table and write “None”.

Number	Document reference number	Date	Title
1	1	January 24, 2023	Annex Code Tables

ANNEX 2. ENCEPP CHECKLIST FOR STUDY PROTOCOLS

Not required

## 1. AMENDMENTS FROM PREVIOUS VERSION(S)

Version	Date	Changes	Rationale
1.3	07-Dec-2023	Added 'in the United States' to the title	Reflect protocol amendment
1.3	07-Dec-2023	Added age group and PPSV23 number of doses as potential stratification variables	Reflect protocol amendment
1.3	07-Dec-2023	Updated potential negative control outcomes	Reflect protocol amendment
1.3	07-Dec-2023	Updated opportunistic infections list	Reflect protocol amendment
1.3	07-Dec-2023	Study follow-up now begins six months after the first HIV-related ICD-9-CM or ICD-10-CM code	Reflect protocol amendment
1.3	07-Dec-2023	Removed requirement for six months of continuous enrollment before members' first HIV-related ICD-9-CM or ICD-10-CM code, updated inclusion start date and removed exclusion for individuals with evidence of ART therapy during baseline period	Reflect protocol amendment
1.2	10-Aug-2023	Updated to SOP template version 3.0	
1.2	10-Aug-2023	Added alternate definition of outpatient	Reflect protocol amendment

		candidiasis infection and NDC table	
1.2	10-Aug-2023	Added time-varying covariates for annual HIV viral load testing and annual CD4 cell count testing and their CPT codes. Added time-varying covariates for respiratory virus season.	Reflect protocol amendment
1.2	10-Aug-2023	Study follow-up now begins 90 days after index and at least 90 days of continuous enrolment in medical plans is added to the inclusion criteria	Reflect protocol amendment
1.2	10-Aug-2023	The two outpatient HIV-related codes are now no more than 730 days apart	Reflect protocol amendment
1.2	10-Aug-2023	90 instead of 30-day intervals now used for the analysis of RZV	Needed due to low numbers of patients vaccinated with RZV overall and in each interval
1.2	10-Aug-2023	Updated person-time exclusion in Incidence Rates subsection of 7.1 from 29 to 89 days	Needed to reflect the previous update to the number of days separating recurrent events from 30 to 90 days
1.2	10-Aug-2023	Added a definition of overall SMD	Needed for reporting in output table
1.2	10-Aug-2023	Specified cluster robust standard errors for the 95% confidence intervals for the incidence rates based on recurrent events and updated R code	Needed to account for multiple events per patient

1.2	10-Aug-2023	Updated Payor categories in Table 5.2	Previous categories did not accurately represent the values in the database
1.2	10-Aug-2023	Added text and reference to potentially correct main results for any bias identified from the negative control outcome	Needed to clarify the potential calculation that will be used
1.1	2-Jun-2023	The number of days used to separate pneumonia and candidiasis episodes to identify independent events was increased from 30 to 90 days.	Unrealistically high numbers of recurrent events were generated for several patients when using 30 days. It was therefore decided that 30 days may be insufficient time to recover from these infections in a HIV population. This decision was taken prior to generating incidence rates by vaccination status and prior to generating vaccine effectiveness results using recurrent events.
1.1	2-Jun-2023	Included the reporting of incidence rates annually and during the time periods of interest.	Added to explore potential changes over time.
1.1	2-Jun-2023	Specified that covariates imbalanced after weighting may be included in final weighted models.	Added to clarify the purpose of the assessment of covariate balance.
1.1	2-Jun-2023	Updated example code for standardized differences	Fixed error in code to match description.
1.0	20-Mar-2023	N/A. First version	N/A

## 2. LIST OF ABBREVIATIONS

Abbreviation	Definition
AG	Andersen-Gill
ART	Antiretroviral therapy
ATE	Average treatment effect
CI	Confidence interval
Cox-MSM	Marginal structural Cox models
CPT	Current procedural terminology®
CSF	Cerebrospinal fluid
HIV	Human immunodeficiency virus
HR	Hazard ratio
ICD-9-CM	International Classification of Diseases, Ninth Revision, Clinical Modification
ICD-10-CM	International Classification of Diseases, Tenth Revision, Clinical Modification
ICD-9-PCS	International Classification of Diseases, Ninth Revision, Procedure Coding System
ICD-10-PCS	International Classification of Diseases, Tenth Revision, Procedure Coding System
IPCW	Inverse probability of censoring weighting
IPD	Invasive pneumococcal disease
IPTW	Inverse probability of treatment weighting
NDC	National Drug Code
NI	Non-interventional

PCV	Pneumococcal conjugate vaccine
PCV13	13-valent pneumococcal conjugate vaccine
PPSV23	23-valent pneumococcal polysaccharide vaccine
PLWH	People living with HIV
RZV	Recombinant zoster vaccine
SMD	Standardized mean differences
SVI	Social Vulnerability Index
VE	Vaccine effectiveness

Note: in this document, any text taken directly from the non-interventional (NI) study protocol is *italicized*.

### 3. RATIONALE AND BACKGROUND

People living with HIV (PLWH) are at increased risk of pneumococcal infections, but there is a lack of data on 13-valent pneumococcal conjugate vaccine (PCV13) vaccine effectiveness (VE) in PLWH.

The purpose of this study is to estimate PCV13 VE against pneumococcal disease in PLWH aged  $\geq 18$  years, overall and, if feasible, at 3, 5, and 7 years of follow-up. The primary outcomes of interest are invasive pneumococcal disease (IPD), pneumococcal pneumonia and all-cause pneumonia.

### 4. STUDY OBJECTIVES AND HYPOTHESES

#### 4.1. Primary Objectives

*The primary objectives of this study are:*

1. *Estimate vaccine effectiveness (VE) of PCV13 for invasive pneumococcal disease (IPD) among people living with HIV (PLWH)  $\geq 18$  years of age, overall and, if feasible, at 3, 5, and 7 years of follow-up*
2. *Estimate VE of PCV13 for pneumococcal pneumonia among PLWH  $\geq 18$  years of age, overall and, if feasible, at 3, 5, and 7 years of follow-up*
3. *Estimate VE of PCV13 for all-cause pneumonia among PLWH  $\geq 18$  years of age, overall and, if feasible, at 3, 5, and 7 years of follow-up.*

